7.3 Subject Population(s) for Analysis

Protocol-compliant population: Any subject who participated and received the protocol required study drug exposure.

8 Safety and Adverse Events

8.1 Definitions

Unanticipated Problems Involving Risk to Subjects or Others (UPIRTSO)

Any unanticipated problem or adverse event that meets the following three criteria:

- Serious: Serious problems or events that results in significant harm, (which may be physical, psychological, financial, social, economic, or legal) or increased risk for the subject or others

(including individuals who are not research subjects). These include: (1) death; (2) life threatening adverse experience; (3) hospitalization - inpatient, new, or prolonged; (4) disability/incapacity - persistent or significant; (5) birth defect/anomaly; (6) breach of confidentiality and (7) other problems, events, or new information (i.e. publications, DSMB reports, interim findings, product labeling change) that in the opinion of the local investigator may adversely affect the rights, safety, or welfare of the subjects or others, or substantially compromise the research data, AND

- Unanticipated: (i.e. unexpected) problems or events are those that are not already described as potential risks in the protocol, consent document, not listed in the Investigator's Brochure, or not part of an underlying disease. A problem or event is "unanticipated" when it was unforeseeable at the time of its occurrence. A problem or event is "unanticipated" when it occurs at an increased frequency or at an increased severity than expected, AND
- Related: A problem or event is "related" if it is possibly related to the research procedures.

Adverse Event

An untoward or undesirable experience associated with the use of a medical product (i.e. drug, device, biologic) in a patient or research subject. Adverse events are classified as serious or non-serious.

Serious Adverse Event

An adverse event or suspected adverse reaction is considered "serious" if, in the view of either the investigator or sponsor, it results in any of the following outcomes:

- death
- Is considered a life-threatening adverse event
- inpatient hospitalization or prolongation of existing hospitalization
- a persistent or significant incapacity or substantial disruption of the ability to conduct normal life functions
- a congenital anomaly/birth defect.

Important medical events that may not result in death, be life-threatening, or require hospitalization may be considered serious when, based upon appropriate medical judgment, they may jeopardize the patient or subject and may require medical or surgical intervention to prevent one of the outcomes listed in this definition.

All adverse events that do not meet any of the criteria for serious, should be regarded as **non-serious adverse events**.

Adverse Event Reporting Period

For this study, the study treatment follow-up period is defined as three (3) days following the last administration of study treatment, based on 2 hour half-life of EPI.

Preexisting Condition

A preexisting condition is one that is present at the start of the study. A preexisting condition should be recorded as an adverse event if the frequency, intensity, or the character of the condition worsens during the study period.

General Physical Examination Findings

At screening, any clinically significant abnormality should be recorded as a preexisting condition. At the end of the study, any new clinically significant findings/abnormalities that meet the definition of an adverse event must also be recorded and documented as an adverse event.

Post-study Adverse Event

All unresolved adverse events should be followed by the sponsor-investigator until the events are resolved, the subject is lost to follow-up, or the adverse event is otherwise explained. At the last scheduled visit, the sponsor-investigator should instruct each subject to report, to the sponsor-investigator any subsequent event(s) that the subject, or the subject's personal physician, believes might reasonably be related to participation in this study.

Abnormal Laboratory Values

A laboratory abnormality should be documented as an adverse event if the laboratory value remains outside of the normal range on repeat testing and the subject's personal physician or PI, believe might reasonably be related to study medication. If the subject's personal physician or PI considers the laboratory abnormality unsafe/clinically significant, the study treatment might be discontinued. If the laboratory abnormality is considered treatable, it will be treated appropriately. The laboratory abnormality will be followed until it normalizes or no longer is considered unsafe and needing a follow up.

Hospitalization, Prolonged Hospitalization or Surgery

Any adverse event that results in hospitalization or prolonged hospitalization should be documented and reported as a serious adverse event unless specifically instructed otherwise in this protocol. Any condition responsible for surgery should be documented as an adverse event if the condition meets the criteria for an adverse event.

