Telephone calls between baseline and 3 month on-site visits: The subjects/LAR will be contacted by study staff approximately every 15 days to assess progress, symptoms and dosing compliance. If it appears subject is experiencing adverse changes and the Investigator feels an on-site visit is warranted, the subject will be asked to come in for an interim clinic visit.

Visit 2: Week 12 (+/- 1 week)

At Visit 2, the participant will undergo a physical exam and FARS scoring. Medical history, changes to concurrent medications, adverse event diary and dosing will be reviewed and additional diaries dispensed, as needed. A physical examination will be conducted. Dosing of (+)- EPI will be adjusted depending on the performance of the 8m timed walk completed through the FARS assessment and/or cardiac assessment via MRI. If the participant shows improvement (as defined in section 3.1) compared to baseline in composite score, including the 8m timed walk or cardiac function by MRI, the medication dosage will remain the same. If the participant shows no improvement or worsening compared to baseline, the (+)- EPI dose will be increased. Additional investigations include:

- Physical Examination, Vitals, Blood Pressure
- Drug level analysis of (+)- EPI in blood
- FARS Assessment
- Blood chemistry
 - Serum BNP, calcium, cardiac troponin I, CBC, ceruloplasmin, creatinine with eGFR, frataxin, , hemoglobin A1C, iron, mitochondrial complex I-V, potassium, PT/PTT, sodium, and ST2, triglycerides, and liver panel (ALT, AST, and Alkaline Phosphatase)
- Cardiac MRI with BOLD
- Urine pregnancy test

Telephone calls between 3 month and 6 month on-site visits: The subjects/LAR will be contacted by study staff approximately every 15 days to assess progress, symptoms and dosing compliance. If it appears subject is experiencing adverse changes and the Investigator feels an on-site visit is warranted, the subject will be asked to come in for an interim clinic visit.

Visit 3: Final Evaluation- Week 24 (+/- 1 week)

At the final visit, the participant will undergo a physical exam and neurological/cardiac assessments. Changes in symptoms and any concurrent medications will be assessed and the dosing/adverse event diary will be reviewed and collected/retained. Final investigations include:

- Physical Examination, Vitals, Blood Pressure FARS Assessment
- Urine analysis: F2-isoprostane
- Blood sample(s)
 - Analysis of (+)- EPI drug level and follistatin/myostatin levels

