3.5 Primary Safety Endpoints

Safety endpoints will include:

- Distribute a diary to each study participant in order to date and record symptoms of adverse events along with drug intake. All participants will be asked to contact study coordinator or PI via phone in the case of an adverse event, which will then be documented in the source documents. Participants will be asked to bring the diary along with their drug bottles to each clinic visit.
- Comparison between treatment groups of the incidence and types of reported adverse events including increase in migraine headaches, bruising or bleeding.

The consumption of cocoa products containing the epicatechins has been reported to be associated with increased likelihood of migraine development [37]. However, the migraine effect has not been validated in subsequent clinical trials, and, if it exists, has been attributed to the presence of phenylethylamine [38].

Anti-clotting like effects have been described for foods containing members of the flavonoid family including epicatechin, such as cocoa, tea, and guarana. There is no report as to the effects that epicatechin per se may have on phenomena such as platelet aggregation or clotting times [14, 38, 39].

The modest effects on platelet aggregation of food containing polyphenols has been cited as one basis for beneficial cardiovascular effects. To our knowledge, no adverse

event involving platelet inhibition has been described in any study of foods or their extracts of cocoa, guarana, or tea. Nonetheless, we deemed it prudent to exclude patients with thrombocytopenia or clotting disorders.

- Potential risk based on the biological activities of (+)-epicatechin includes hypotension through presumed mechanism of nitric oxide (NO) mediated vasodilation [40]. Of note is the fact that so far, no blood pressure reducing effects by (-)-epicatechin have been reported in normotensive subjects. With cocoa based studies, blood pressure reducing effects are only reported in humans that have high blood pressure [41]. In the study by Ottaviani et al., the vasodilating effects of (+)-epicatechin in humans were only 25% of those of (-)-epicatechin when given at the same doses (1.5 mg/kg) [21]. There is the possibility that patients undergoing pharmacologic treatment for high blood pressure if given epicatechin may develop hypotension through additive or synergistic effects.

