4.4 Withdrawal of Subjects

4.4.1 When and How to Withdraw Subjects

Subject Withdrawal Criteria

- The end of the trial for a patient will be defined for this study as (1) completion of the final 24 week evaluation, (2) death, (3) withdrawal of consent, (4) if the patient is lost to follow-up at 12 weeks clinic visit, the date of the patient's last visit for which data is available.
- Patients may be withdrawn from this trial for the reasons provided below:

Withdrawal for Adverse Event

- A patient who experiences an adverse event during the study drug administration that the Investigator judges to be related to the study drug and poses a significant risk to the patient will have the study drug discontinued. All scheduled data will be collected and the patient will be included in all safety analyses.

Withdrawal of Consent

- Patients for whom Informed Consent is withdrawn will have study drug discontinued (if the decision occurs during the study period). No further data collection will be done without written consent for follow-up data collection. All available data on these patients will be included in the safety analyses.
- Investigator Decision to Withdraw Patient Should the Investigator determine that it is in the best interest of a patient to be withdrawn from the trial, the drug will be immediately discontinued (if the decision occurs during the study period). All scheduled data deemed appropriate by the Investigator will be collected and the patient will be included in all safety analyses.
- Pregnancy; If a subject's pregnancy test is positive at 12 weeks, subject will be discontinued from further study participation and any dispensed study medication will be retrieved from the subject. Subject and child will be followed for potential adverse effects of study drug dosing.

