5.6 Packaging

25 mg capsules of open-label study medication will be packaged 42 capsules per bottle. The bottles will be subsequently labeled by the Research Pharmacy for each subject, based on a written prescription by a Study Investigator. A 3 month supply will be dispensed at the Baseline visit and again at the 3 month visit, as specified in Section 3.1. An overage amount (2 week supply) will be dispensed to allow for flexibility in visit scheduling.

In addition to dosing directions, the bottles shall bear a label with the statement "*Caution: New Drug--Limited by Federal (or United States) law to investigational use.*"

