8.2 Recording of Adverse Events

During each contact with the subject, the study team will seek information on adverse events by specific questioning and, as appropriate, by examination. Information on all adverse events should be recorded in the source document, and also in the appropriate adverse event section of the case report form (CRF) or in a separate adverse event worksheet. All changes in symptoms, and diagnostic, laboratory or procedure results that potentially are considered related to study medication should be recorded in the source documents. The subject's AE diary will be considered a study source document and retained by the site within the subject's study file for monitoring and inspectional purposes.

All adverse events occurring during the study period will be recorded. The clinical course of each event will be followed until resolution, stabilization, or until it has been ultimately determined that the study treatment or participation is not the probable cause. Serious adverse events that are still

ongoing at the end of the study period must be followed, to determine the final outcome. Any serious adverse event that occurs after the study period and considered to be at least possibly related to the study treatment or study participation should be recorded and reported immediately.

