Attachment II
Protocol Schedule of Event

^a (+)-EPI drug levels and follistatin/myostatin levels will be analyzed by UC-San Diego. All other laboratory analyses will be conducted by Mayo Clinic Department of Lab Medicine and Pathology and Research Laboratories

15-006845 Protocol Schedule of Events						
Study Activity	Week 0 Baseline Clinic Visit	Interim Contacts	Week 3 (+/- 1 week) Lab Only	Week 12 (+/- 1 week) Clinic Visit	Interim Contacts	Week 24 (+/- 1 week) Clinic Visit
Visit	1			2		3
Review Eligibility	X					
Informed Consent	X					
Medical History	X			X		X
Concurrent Medications	X			X		X
Physical Exam/Vitals/BP	X			X		X
Drug Level (+)- EPI ^a	X		X	X		X
Follistatin/Myostatin ^a	X		X			X
Blood labs ^b	X			X		X
Urine Analysis ^c	X					X
Neuro Studies ^d	X					X
Cardiac MRI/BOLD	X			X		X
Echo/ECG/Perfusion MRI	X					X
FARS Assessment	X			X		X
Urine Pregnancy Test ^e	X			X		X
Dispense Study Med Dosing/AE Diary ^f	X			X		
Increase Dose, if appl ^g				X		
Review Dosing and AE diary				X		X (collect)
Interim Contacts ^h		X			X	
Off-study evaluation ⁱ	X					X

^a (+)-EPI drug levels and follistatin/myostatin levels will be analyzed by UC-San Diego. All other laboratory analyses will be conducted by Mayo Clinic Department of Lab Medicine and Pathology and Research Laboratories

^b: Serum BNP, Calcium, cardiac troponin I, Complete Blood Count (includes RBCs, WBCs with differential, platelets), ceruloplasmin, creatinine with eGFR, frataxin, glucose tolerance test (not performed week 12), hemoglobin A1C, iron, mitochondrial complex I-V, potassium, PT/PTT, sodium, ST2, triglycerides, liver enzymes (AST, ALT, Alk phos)

^c: F2-isoprostane

^d: Magnetic resonance imaging of cerebellum and spinal cord, magnetic resonance spectroscopy

^e: Urine pregnancy test (females of childbearing potential)

^f: (+)- EPI orally administered daily for 24 weeks

^g: (+)-EPI dose will be increased from 75mg/day to 150mg/day, if 8m timed walk via FARS assessment or cardiac evaluation shows no improvement or worsens

^h: Study site staff will contact the subject/LAR approximately every 15 days between the Baseline, Week 12 and Week 24 visits to assess clinical changes, adverse events and dosing compliance.

ⁱ. Respiratory chain function, aconitase, catalase, PGC1 α , SOD2 in blood if needed

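### The 3-day adverse-event period after the last EPI dose has no scheduled contact after the week-24 visit, and nor do the days after the final stress scan; one closing call would cover both

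*Combined protocol and SAP*

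**What the plan says.** Section 8.1, under Adverse Event Reporting Period, defines follow-up as "three (3) days following the last administration of study treatment, based on 2 hour half-life of EPI".

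Scheduled contact ends with the week-24 visit. Attachment II, footnote h, says "Study site staff will contact the subject/LAR approximately every 15 days between the Baseline, Week 12 and Week 24 visits", and its last column is the week-24 clinic visit. At that visit (Section 3, Visit 3) "the dosing/adverse event diary will be reviewed and collected/retained". The same visit includes cardiac MRI with perfusion, which Section 3.4 identifies as a regadenoson stress study.

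On drug supply, Section 5.6 says "An overage amount (2 week supply) will be dispensed to allow for flexibility in visit scheduling".

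Several provisions on adverse events sit alongside the 3-day period:

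- Section 3.5: "All participants will be asked to contact study coordinator or PI via phone in the case of an adverse event".
- Section 8.2: "During each contact with the subject, the study team will seek information on adverse events by specific questioning".
- Section 8.1, Post-study Adverse Event: at the last visit, subjects are told to report later events that they or their own physician think may be related to taking part. Unresolved events are followed.
- Section 8.2: a serious event after the study period that is "considered to be at least possibly related to the study treatment or study participation should be recorded and reported immediately".
- Section 4.4.1, for a subject taken off drug for a related adverse event: "All scheduled data will be collected and the patient will be included in all safety analyses".

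**The concern.** The plan defines a period in which adverse events count but gives staff no scheduled occasion to ask about them. During treatment, adverse events are sought in three ways: clinic questioning, a diary, and calls about every 15 days. After the week-24 visit all three stop. What remains relies on the subject to start the contact, and the last-visit instruction also relies on a judgement of cause made before the investigator hears of the event.

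The same visit is the last exposure to regadenoson and, as inferred from the late gadolinium enhancement endpoint in Section 3.2, to gadolinium. Calls that ask about adverse events follow the baseline and week-12 scans. None follows the week-24 scan.

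Safety is part of the primary objective (Section 2), and the trial has ten subjects and no control arm. One subject is 1/10 = 10 percentage points of any incidence, so even a single unreported event would be visible in the safety table.

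**Working it through.** **1. Is 3 days long enough for the drug?** Section 1.2 gives half-lives of 1.8 to 3.8 h for (-)-EPI and under 1.5 h for both enantiomers; Section 8.1 uses 2 h. Three days is 72 h.

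- 72 / 2 = 36 half-lives
- 72 / 3.8 = 18.9 half-lives
- 72 / 1.5 = 48 half-lives

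The length is ample for washout. The question is only whether anyone asks during it.

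**2. Completers: how much of the period follows the last contact?** Treatment is 24 x 7 = 168 days. The final visit is at 168 +/- 7, so day 161 to 175. The protocol does not fix the last-dose date, so both plausible patterns are shown.

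| Last dose | Visit day | Period closes | Days of the period after the visit |
|---|---|---|---|
| Day of visit | 161 to 175 | 164 to 178 | 3 |
| Day 168 | 169 | 171 | 2 |
| Day 168 | 170 | 171 | 1 |
| Day 168 | 171 | 171 | 0 |
| Day 168 | 172 to 175 | 171 | 0 (the visit asks in retrospect) |

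The overage and the drug level drawn at week 24 point to the first row but do not settle it. For ten completers the uncovered total runs from 10 x 0 = 0 to 10 x 3 = 30 subject-days. At its largest this is 3 of 168 + 3 = 171 days per subject, or 1.8%.

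**3. After the final scan.** Attachment II places perfusion MRI at baseline and week 24 only. For ten completers that is 2 x 10 = 20 regadenoson administrations, of which 10 (50%) are at the last visit. The lead bullet of Section 3.4 also mentions week 12; if that were counted, the share would be 10/30 = 33%. Scheduled contacts after the last administration: none. This result does not depend on the last-dose date.

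**4. What each remaining provision catches after week 24.**

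| Provision | Who starts it | Limited by cause? | Limited to serious events? |
|---|---|---|---|
| Phone instruction (3.5) | Subject | No | No |
| Last-visit instruction (8.1) | Subject | Yes, as subject or own physician sees it | No |
| Late serious events (8.2) | Not stated | Yes, at least possibly related | Yes |
| Follow-up of unresolved events (8.1, 8.2) | Study team | No | No, but only events already known |

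The uncovered case is a new, non-serious event that the subject does not volunteer.

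**5. Cost of one more call.** Each interval between visits is 84 days, and 84 / 15 = 5.6, so 5 to 6 calls. Two intervals give 10 to 12 per subject, or 100 to 120 for ten completers. Ten more is 10/120 = 8.3% to 10/100 = 10%.

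**The case against.** The strongest reply is that little is lost. Three days is many half-lives, so a late effect of EPI is unlikely. Serious events that are possibly related must be reported whenever they occur. The last-visit instruction refers to taking part in the study and not only to the drug, so it reaches reactions to the scan agents. Subjects are screened for contraindications to both agents (Sections 4.1, 4.2). A reaction to an imaging agent also says little about EPI, which is what the primary safety objective concerns. Finally, existing calls come about every 15 days, so no day-3 call follows the earlier scans either.

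Most of this stands, and it keeps the point small. It does not remove it. The instructions are passive, and after the earlier scans a later call at least asks in retrospect, whereas after week 24 none does. Section 8.1 also counts research procedures when defining related unanticipated problems, so the plan's own safety remit is wider than EPI.

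A reader might infer something stronger about subjects who stop EPI early. With a last dose on day 84, the 3-day period closes on day 87, which is 74 to 88 days before a scan on day 161 to 175. It is tempting to conclude that events around that scan fall outside adverse-event recording. The documents do not support this. Section 8.1 does not say that recording stops when the 3 days end. Section 4.4.1 ends the trial for a patient at the final evaluation, and stopping drug is not listed as an end. Section 8.2 records all events in the study period and asks at every contact. The study period is not defined, but these sections can be read together as keeping early stoppers under recording to week 24. After that visit they share the same lack of contact as everyone else.

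**Conclusion.** The point holds as a gap in scheduled follow-up. No contact is scheduled after the week-24 visit, so up to all 3 days of the defined period, and in every case the days after the final scan, rest on the subject to report.

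For ten completers the size is 0 to 30 subject-days, depending on when the last dose falls. A reader might take the upper figure as certain. It is not, because it requires every last dose to fall on or after the visit day, which the overage suggests but the protocol does not fix. Nor do the documents support saying that serious related events would be lost, or that 3 days is too short for the drug.

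The likely loss is confined to non-serious events. The documents give no reaction rates or timing for EPI, regadenoson or gadolinium, so the under-count cannot be estimated and is probably small. No efficacy estimate, test or stopping rule is affected. This is a cheap improvement to consider.

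**What to change.** In Attachment II, add one telephone call of the existing type about 3 days after the later of the last EPI dose or the week-24 visit. Make it for every subject who attends that visit, including those who stopped EPI early, unless consent to follow-up is withdrawn. Ask about all adverse events whatever the believed cause. Three days reuses the plan's own length, since the documents give no timing for the imaging agents.

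In Section 8.1, state that the adverse-event reporting period runs to that call. The wording change alone would collect no data; the call is what matters.

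The cost is one sentence, one schedule entry and about ten short calls on top of roughly 100 to 120, plus one for each early stopper who attends week 24. Dosing, imaging and the stopping rules are unchanged.

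### Section 8.1 makes persistence and suspected drug-relatedness conditions for recording a laboratory adverse event, so the laboratory part of the safety endpoint can be under-recorded

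*Combined protocol and SAP*

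**What the plan says.** The laboratory rule is in section 8.1, under Abnormal Laboratory Values. Its first condition is persistence: "A laboratory abnormality should be documented as an adverse event if the laboratory value remains outside of the normal range on repeat testing". The word *and* joins it to a second condition, that the subject's "personal physician or PI, believe might reasonably be related to study medication".

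The next sentence deals with more serious values. If either physician "considers the laboratory abnormality unsafe/clinically significant, the study treatment might be discontinued". The paragraph goes on to treatment and follow-up of the abnormality. It does not say that such a value is recorded as an adverse event.

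The general definition, also in section 8.1, is wider: "An untoward or undesirable experience associated with the use of a medical product (i.e. drug, device, biologic) in a patient or research subject".

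Section 8.2 says that "All adverse events occurring during the study period will be recorded". For laboratory findings it also says that "laboratory or procedure results that potentially are considered related to study medication should be recorded in the source documents".

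Section 3.5 gives the safety endpoint as the "incidence and types of reported adverse events including increase in migraine headaches, bruising or bleeding". Section 5.7 confirms that the drug is open label, and the Study Summary gives no reference therapy.

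**The concern.** Whether an abnormality persisted, and whether someone thinks the drug caused it, are attributes of an event. Here they decide whether a laboratory finding becomes an event at all. A clinically significant value that is transient, is not repeated, or is put down to the disease has no stated laboratory route into the count of reported adverse events.

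Three features of this trial make that matter.

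- **Attribution is hard.** Section 1.1 describes cardiomyopathy and diabetes as frequent in this disease, so an abnormal troponin, BNP or glucose is easily ascribed to it. With no control arm, nothing in the trial tests that opinion. A complete count is the better basis for judging the drug.
- **Laboratory findings bear on a named risk.** Section 3.5 lists bruising and bleeding, and section 4.2 excludes thrombocytopenia and prolonged PT/PTT at baseline. A PTT newly prolonged on treatment, but judged unrelated or not repeated, would have no stated laboratory route into the endpoint.
- **The sample is about 10 subjects.** One or two unrecorded cases change the reported incidence materially.

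**Working it through.** **1. The rules side by side.**

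| Kind of finding | Place | Repeat test needed? | Physician's opinion on cause needed? |
|---|---|---|---|
| Any adverse event (general definition) | 8.1 | No | No |
| Worsened preexisting condition | 8.1 | No | No |
| New clinically significant physical finding | 8.1 | No (must meet the general definition) | No |
| Laboratory abnormality | 8.1 | Yes | Yes |

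Only laboratory values face both conditions. The general definition speaks of association with use of the product, but asks for no opinion on cause.

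**2. Does section 8.2 repair this?** No. Its statement that all adverse events are recorded takes the definition as given. Its sentence on source documents applies a relatedness condition to laboratory results again.

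**3. Is a repeat value available?** The safety laboratory tests are listed at weeks 0, 12 and 24 (Attachment II). The week 3 draw covers only drug level and follistatin/myostatin. A week 12 abnormality is redrawn at week 24. A new one at week 24 has no later scheduled draw, and section 8.1 sets treatment follow-up at three days after the last dose. Section 8.1 does say that abnormalities are followed until they normalise or are no longer considered unsafe. That implies unscheduled retesting, but sets no timing.

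**4. Would the analysis show what the rule leaves out?** Section 7.2 provides generic descriptive summaries. It names no laboratory shift table and no listing of out-of-range values.

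**5. Illustration of size.** The plan gives no figure for laboratory abnormality rates or capture, so there is none to reproduce. Inputs:

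- n = 10, the target in section 4.5.
- p, the true share of subjects with a clinically significant abnormality: assumed, 10% to 30%.
- q, the share of those that meet both conditions: assumed, 25% to 100%.
- Subjects are taken as independent.

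The recorded rate is p × q, and P(at least one recorded) = 1 − (1 − pq)^10.

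At p = 20%:

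- q = 100%: 1 − 0.80^10 = 0.893
- q = 75%: 1 − 0.85^10 = 0.803
- q = 50%: 1 − 0.90^10 = 0.651
- q = 25%: 1 − 0.95^10 = 0.401

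Over the range of p:

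| p | q = 100% | 75% | 50% | 25% |
|---|---|---|---|---|
| 10% | 65.1% | 54.1% | 40.1% | 22.4% |
| 20% | 89.3% | 80.3% | 65.1% | 40.1% |
| 30% | 97.2% | 92.2% | 80.3% | 54.1% |

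**6. What a clean result would mean.** If none of 10 subjects has a recorded case, the one-sided 95% upper bound on the recorded rate is 1 − 0.05^(1/10) = 25.9%. Dividing by q gives the bound on the true rate: 25.9% at q = 100%, 34.5% at 75% and 51.8% at 50%. At 25% the quotient exceeds 100%, so the result says nothing.

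**The case against.** The strongest reply is that the clause is narrower than it looks. Several parts of it stand.

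- **The text says *if*, not *only if*.** A reader might infer that an unattributed abnormality can never be counted. The documents do not support that. A worsened preexisting condition, an important medical event or an event leading to hospitalisation can bring the associated problem in by another route. What remains is that no other *laboratory-specific* route is stated.
- **Laboratory incidence is not the whole safety result.** A reader might infer that it is, because there is no control arm. Section 3.5 counts all reported adverse events and names symptoms. Events from diaries, questioning and telephone contacts do not pass through this clause.
- **The data are not lost.** Scheduled values are collected whatever anyone thinks of their cause. BNP, troponin and ST2 are analysed as changes from baseline under section 3.2. The gap is in what counts as an adverse event and in the absence of a named safety summary.
- **An open-label opinion on cause is unavoidable.** With no comparator it cannot differ between arms, and the threshold (might reasonably be related) is low. The weakness lies in using the opinion as an entry condition.
- **The current rule also counts mild values.** A persistent, possibly related value that is only slightly out of range is an adverse event today. Replacing the rule with clinical significance alone would drop it, and the net direction of change would be unclear. The fix must therefore add to the present set.

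The objection does not explain why a value serious enough for treatment to be stopped has no stated route to being recorded as an adverse event.

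**Conclusion.** The point holds in a limited form. Applied as written, section 8.1 can under-record the laboratory-derived part of the safety endpoint. Section 8.2 does not correct this, and the general definition in section 8.1 does not impose the same conditions.

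The direction is clear only for clinically significant abnormalities that fail one of the two conditions: they have no stated laboratory route into the count. The amount is unknown. The drop from 89% to 65% or 40% in the chance of recording at least one case rests on an assumed 20% true rate and assumed capture of 50% or 25%. Nothing in the documents shows that half or three quarters of such findings would be screened out, so these figures should not be read as an estimate of bias.

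This should be corrected because it affects how a low adverse-event count would be read. It does not undermine the efficacy analyses or the symptom data.

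**What to change.** 1. Reconcile the general definition and the laboratory paragraph in section 8.1 with section 8.2, so that relatedness is not a condition for recording.
2. Record as an adverse event any clinically significant laboratory abnormality, whether or not it was repeated or thought related. Keep the persistent, possibly related out-of-range values that the present rule counts. The new set then contains the old one.
3. Capture persistence and relatedness as separate fields on the adverse-event record, so that results can be reported with and without them.
4. Remove the relatedness condition on recording laboratory results in source documents in section 8.2.
5. Add to section 7.2 a shift table from baseline to worst value, and a by-subject listing of out-of-range values, for the scheduled safety laboratory tests.

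The cost is a few more adverse-event entries, one table and one listing. No test or visit is added, and no clinical management rule needs to change.
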